**Exclusion criteria:**

- Any patient under 18 years of age.
- Any patient with an active thromboembolic event (within the last 24 hours) – i.e. active stroke, myocardial infarction or pulmonary embolism.
- Any patient with a hypersensitivity or anaphylactic reaction to TXA.
- Any patient more than three-hour post injury.
- Traumatic arrest with > 5 minutes CPR without return of vital signs
- Penetrating cranial injury
- Traumatic brain injury with brain matter exposed
- Isolated drowning or hanging victims
- Documented cervical cord injury with motor deficit

**Study Drug:**

Tranexamic acid
------------------------

Tranexamic acid (trade name Cyklokapron, Lysteda) is a synthetic derivative of the amino acid lysine. TXA blocks the formation of plasmin from plasminogen and, at high concentrations, noncompetitively inhibits plasmin. Plasmin is a molecule that triggers clot breakdown. TXA is excreted renally. The use of TXA as a supplement has been successful in the control of bleeding in hemophilia, preoperatively, gastric hemorrhage, menorrhagia, traumatic hyphema and in the treatment of hereditary angioedema. TXA is supplied in 1000mg ampules in 10mL normal saline.

**Side effects:**

- Acute gastrointestinal disturbances (nausea, vomiting and diarrhea; generally dose-related).
- Visual disturbances (blurry vision and changes in color perception, especially with prolonged use).
- Thromboembolic events (deep venous thrombosis, pulmonary embolism).
- Dizziness, fatigue, headache, and hypersensitivity reaction.
- Seizures (only observed in high concentrations of TXA)

**Administration and route:**

- Administer 1 gram of TXA in 100 ml of 0.9% Normal Saline, intravenous or via interosseous device over 10 minutes as soon as possible but no later than three hours after injury.
- Infuse a second gram of TXA IV or IO over 8 hours in 0.9% Normal Saline.
- TXA SHOULD NOT be administered through same line as blood products, rfactor VIIa, or Hexend.
- DO NOT administer as IV push, may cause hypotension.
- Drug must be stored at 59-86 degrees Fahrenheit.

- Clearly identify the patient who received TXA with an approved red wristband prior to transporting the patient to a regional trauma center participating in the study.

### **Considerations:**

TXA is a synthetic derivative of the amino acid lysine and is not a blood product or a blood replacement product. Therefore, there should be no restrictions to TXA administration based on social or religious objections.

### **Consent:**

TXA is a FDA approved drug, with a proven safety profile. TXA has an extensive (approximately 40 years) history of utilization in patients with hemophilia, surgical related hemorrhage and bleeding during dental procedures. TXA has also been thoroughly studied (CRASH2 and MATTERS) for safety and efficacy when used in setting of traumatic hemorrhaging.

The current protocol used by designated trauma centers in this study includes the TXA as a standard of care for patients with traumatic hemorrhagic shock as part of their massive transfusion protocol. As a result, any patient fulfilling the inclusion criteria shall fall under emergency medical care act.

### **Data collection:**

Baseline characteristics

- Time of injury to TXA
  - (1st and 2nd dose)
- Demographics: Age, Gender, Race
- Vital Signs: five sets (pre-hospital, during infusion, post-infusion, during second infusion, post-infusion)
  - Heart rate, respiratory rate, body temperature, blood pressure, capillary refill
- Glasgow Coma Scale (pre-treatment, 24 hours, 48 hours)
  - ≤8, 9-12, 13-15

### **Analysis Measures**

- Survival at 24 hours, 48 hours, and 28 days
- Cause of death (hemorrhage, other causes)
- Mechanism of injury (blunt, penetrating, combination of blunt and penetration, amputation)

- Area of injury
  - Head, chest, abdomen, extremity, multiple areas
- Blood product Used:
  - Packed red blood cells, fresh frozen plasma, platelets, cryoprecipitate.
- Estimated blood loss
  - Pre-hospital and hospital estimate, operating room estimate, and chest tube output
- Number of transfused unit(s) of blood products (<2 units, 2-4 units, >4 units i.e. massive transfusion.
- Time to emergency care: Time from EMS encounter to emergency department (ED), time spent in emergency department, time from ED arrival to operating room.
- Hospital length of stay: Intensive care unit length of stay, discharge disposition
- Ventilator days
- Adverse side effects, thromboembolic, seizures
- Deep venous thrombosis prophylaxis timing
- Result of drug test and medications that may falsely alter patients pulse during the initial evaluation and resuscitation

#### **Statistical analysis:**

- Based on a 0.95 confidence level and a 10% margin of error, the target would be 200 patients in each group.
- Statistical tests: Two-tailed T Test, Regression Analysis, Chi-Square Analysis

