**Purpose:**

To determine if pre-hospital administration of TXA in trauma patients with signs of hemorrhagic shock provides for a statistically significant decrease in mortality, total blood product usage and total estimated blood loss, without a significant increase in thromboembolic complications.

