### **Background:**

Trauma is one of the leading causes of death amongst people aged 16-35. First responders have limited resources for resuscitation of hemorrhagic shock. TXA is an anti-fibrinolytic that inhibits the activation of plasminogen to plasmin, an enzyme that dissolves blood clots. It has historically been used to minimize blood loss in planned surgeries such as orthopedic and cardiac surgery, control oral bleeding in patients with hemophilia, and treat heavy menstrual periods. [1,2] An inexpensive pharmacologic agent, TXA may have a practical use in the pre-hospital setting of trauma-related hemorrhage.

The CRASH-2 trial, a 20,000 patient randomized study published in 2010, demonstrated a 1.5% reduction in all-cause mortality at 28 days. [3] This study primarily examined civilian blunt trauma injuries in which TXA was administered within 8 hours of injury. This trial confirmed the safety of TXA in trauma-related injuries given within 3 hours of their traumatic injuries.

At present time, TXA is being widely used in combat related injuries. The MATTERS study published in 2012 examined TXA use in combat injuries requiring at least 1 unit of blood in Afghanistan at the Bastion Role 3 facility. [4] This retrospective, cohort study demonstrated findings supportive of TXA in severely injured, actively bleeding patients. Although there was no overall survival benefit at 24 hours, a survival benefit was seen in patients requiring massive transfusion improving survival at 48 hours by 13.1%.

Early administration of TXA to decrease trauma related mortality has also been established. In 2011, a subgroup analysis of the CRASH-2 Trial proved early treatment with TXA less than one hour from injury resulted in a 2.4% decrease in death. Interestingly, there was a 1.3% increased risk of death due to bleeding in patients who received TXA after 3 hours from injury. [5] Another CRASH-2 economic subset analysis highlighted the fact that TXA can be highly-cost effective. [6]

Applying what we know from these major trials, TXA should have significant benefit in the pre-hospital setting. Two recent small trials have demonstrated that pre-hospital administration of TXA is in fact feasible. [7, 8] By intervening early in trauma related hemorrhage, TXA can improve outcomes and

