#### **Design: Retrospective Comparison and Prospective Cohort Study**

Four groups of patients will be utilized in this study as follows:

**A: Hospital Group:** this group will receive both doses of TXA according to the draft protocol upon arrival to the participating trauma center. No TXA will be given in the field to this patient grouping. 200 patients shall be enrolled in this group in a prospective observational study format.

**B: Air Transport Group:** This group will receive the first dose of TXA according to the draft protocol on scene or during the flight by a licensed flight RN or licensed flight physician. The second dose of TXA will be administered upon arrival at the participating trauma center. 200 patients shall be enrolled in this group in a prospective observational study format.

**C: Paramedic Group:** These patients will receive their first dose of TXA according to the draft protocol in the field by licensed paramedics from participating agencies. The second dose of TXA will be

administered upon arrival at the participating trauma centers. 200 patients shall be enrolled in this group in a prospective observational study format.

**D: Control Group:** 200 patients, transported by ambulance or by air, with similar injury severity and hemodynamics shall be randomly chosen from the previous five years of the trauma registry at the participating trauma center. These patients shall then be compared to Group A, B and C noted above in a retrospective comparison.

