### **Comparisons:**

Groups A, B and C shall be compared to each other in the following format.

1. Hospital/TXA vs. Air Transport/TXA
2. Hospital/TXA vs. Paramedic/TXA
3. Air Transport/TXA vs. Paramedic/TXA
4. Hospital vs. Control Group to validate results of the CRASH-2 Study

All patients receiving TXA should utilize the same inclusion criteria no matter what group they fall into (excluding the control group) to allow for accurate and consistent comparison. All patients in the control group should meet the same inclusion criteria as the patients who received TXA in groups A, B and C.

Patients who fulfill the inclusion criteria will be administered TXA at the participating trauma center or in the field by trained Paramedics, RNs or Flight Physicians from the participating agencies according to the study protocol. The first dose of the TXA (1gm over 10 minutes intravenous or interosseous drip) shall be administered as soon as possible by the hospital or the participating responder teams. A red colored wristband labeled “TXA” attached to their right wrist and/or TXA written on their chest will identify patients who received TXA. Subsequently, upon arrival at the participating trauma center the patients who received TXA will be identified and re-assessed by the trauma team members for hemorrhagic shock. If the patient still meets inclusion criteria, the TXA will be continued at the participating trauma center (1gm over 8 hours intravenous infusion). Patients that meet the inclusion criteria and were not given TXA because they were brought to the emergency department by agencies other than participating agencies will be assigned to the Group A. Administration of TXA is not anticipated to delay patient transport to participating trauma centers. Currently, TXA is part of the mass transfusion protocol at ARMC for patients in traumatic hemorrhagic shock.

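### The 200 per group is a precision figure only: it can neither validate a 1.5-point mortality effect nor make a non-significant thromboembolic test evidence of safety

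*Combined protocol and SAP*

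**What the plan says.** The Statistical analysis section of the combined protocol and SAP gives the whole justification for the size: "Based on a 0.95 confidence level and a 10% margin of error, the target would be 200 patients in each group". It does not say whether the 10% applies to one group's proportion or to a difference between groups, or at what event rate. It states no effect size, power, baseline mortality, thromboembolic rate or margin. The tests follow in one line: "Statistical tests: Two-tailed T Test, Regression Analysis, Chi-Square Analysis". There is no equivalence or non-inferiority analysis.

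Two aims depend on this size:

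- Under Comparisons, item 4 is "Hospital vs. Control Group to validate results of the CRASH-2 Study". The Background says that this 20,000-patient randomized trial "demonstrated a 1.5% reduction in all-cause mortality at 28 days". The Design section says that the control patients "shall be randomly chosen from the previous five years of the trauma registry at the participating trauma center".
- The Purpose seeks significant decreases in mortality, blood product use and blood loss "without a significant increase in thromboembolic complications". Thromboembolic events are a secondary outcome.

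Mortality at 24 hours, 48 hours and 28 days is the primary outcome.

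**The concern.** A margin of error describes how wide an interval will be. The two aims are worded as answers from significance tests, and nothing in the plan links the one to the other. If the precision is several times coarser than the effect to be validated, the hospital-versus-control test says little about that effect in either direction. If a substantial rise in thromboembolic events would often fail to reach significance, the safety part of the Purpose can be met by a result that leaves real harm open. At stake are a false report of non-replication on the primary outcome and false reassurance on the main safety outcome.

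**Working it through.** **Inputs from the plan.** Confidence 0.95, taken as two-sided alpha 0.05 (z = 1.96); margin 10%; 200 per group; mortality effect 1.5 points. **Assumed, because the plan gives none:** control mortality 5-30%, thromboembolic rate 1-5% (10% as a sensitivity case), no dropout.

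**1. The plan's own figure.** For one proportion at 50%: 1.96² × 0.25 / 0.10² = 96.04, so 97. For a difference of two proportions at 50%: 1.96² × 0.50 / 0.10² = 192.07, so 193 per group; with z rounded to 2 it is exactly 200. At 200 per group the half-width of a difference is 1.96 × √(0.50/200) = 9.8 points. So 200 fits a between-group difference in the worst case, rounded up.

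**2. Mortality.** The half-width at a common rate p is 1.96 × √(2p(1−p)/200). Power for p₁ v p₂ = p₁ − 0.015, with p̄ their mean, is Φ[(0.015 − 1.96√(2p̄(1−p̄)/200)) / √((p₁(1−p₁) + p₂(1−p₂))/200)] plus the opposite tail. At 10% mortality: (0.015 − 0.0568)/0.02896 = −1.443, giving 0.0745; the opposite tail adds 0.0066; the total is 8.1%.

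| Assumed control mortality | Half-width (points) | Power for 1.5 points | n per group for 80% power | Least drop giving chi-square p < 0.05 (deaths of 200) |
|---|---|---|---|---|
| 5% | 4.3 | 11.5% | 2,838 | 10 v 3 (3.5 points) |
| 10% | 5.9 | 8.1% | 5,856 | 20 v 9 (5.5) |
| 15% | 7.0 | 7.1% | 8,525 | 30 v 17 (6.5) |
| 20% | 7.8 | 6.7% | 10,844 | 40 v 25 (7.5) |
| 25% | 8.5 | 6.4% | 12,815 | 50 v 34 (8.0) |
| 30% | 9.0 | 6.2% | 14,437 | 60 v 42 (9.0) |

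Counting only significance in the beneficial direction, power is about 5-11%. A significant benefit needs an observed drop of 3.5 to 9 points, which is 3.5/1.5 = 2.3 to 9/1.5 = 6 times the cited effect. The drop detectable with 80% power is 7.0, 8.7, 10.0 and 11.1 points at 10, 15, 20 and 25% mortality.

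**3. Thromboembolic events.** The same formulas apply to a doubling. At 2% to 4%: (0.02 − 0.0334)/0.01703 = −0.789, so power is about 22%. The last column is the chance of excluding a 5-point excess when there is no true difference, Φ(0.05/√(2p(1−p)/200) − 1.96).

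| Assumed rate | Half-width (points) | Power for a doubling | Doubling missed | Chance of excluding 5 points |
|---|---|---|---|---|
| 1% | 2.0 | 13% | 87% | 99.9% |
| 2% | 2.7 | 22% | 78% | 95% |
| 5% | 4.3 | 48% | 52% | 63% |
| 10% | 5.9 | 80% | 20% | 38% |

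For a 2-point excess the chances of exclusion are 52, 30, 15 and 10%.

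**4. Illustration.** Events in 10/200 v 4/200 give an uncorrected chi-square of 2.66, p = 0.10, and a Newcombe 95% interval for the difference of −0.8 to +7.1 points. This would count as no significant increase, yet an excess of 7 points is not excluded.

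**The case against.** Several points on the other side stand.

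- A reader might infer from the one-proportion formula (97) that 200 is an arithmetic error. It is not: the difference formula gives 193, or 200 with z = 2.
- A reader might infer that a 10-point margin makes it impossible to show acceptable safety. That is too strong. Ten points is the worst case at 50%; at thromboembolic rates of 1-5% the half-width is about 2-4 points, and a 5-point excess would be excluded with about 95% probability or more at rates of 1-2%. What can be shown depends on a rate and a margin that the documents do not give. At a 10% rate a doubling would be detected with 80% power.
- A reader might infer that the plan will declare refutation after a null mortality result, or safety after a non-significant one. The Purpose and Comparisons sections state aims, not decision rules, and the documents never say that 200 was chosen to serve either aim.
- The Background also cites larger effects. For 13.1 points, power at 200 v 200 is about 87-99.8% for mortality of 15-30%. That figure, however, comes from massive-transfusion patients at 48 hours and is not the result that comparison 4 names. For the cited 2.4-point early-treatment effect, power is only about 8-24% for mortality of 5-30%.
- The 10 v 4 example is one chosen outcome; the case rests on the power figures.

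None of this supplies the missing link between the sample size and the two aims.

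**Conclusion.** The concern holds in limited form. The mortality part does not depend on the assumed rate: from 5% to 30% control mortality, power for 1.5 points is about 6-12%. A null result would therefore be expected some nine times in ten if the cited effect were true, and a significant result would show a drop well above it. A non-randomized control drawn from earlier registry years is a separate obstacle to validation that more patients would not cure. The thromboembolic part is conditional: at assumed rates of 1-5% non-significance is weak evidence, and no margin is set that would allow a stronger statement. The documents do not support saying that the sample size is wrong or that safety cannot be addressed at 200 per group. This should be fixed before analysis, but it is not a reason to change enrolment.

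**What to change.** Keep 200 per group and revise three sections.

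- **Statistical analysis.** State that the 10% is the worst-case 95% half-width of a between-group difference. Add the half-width and the difference detectable with 80% power over a range of mortality labeled as assumed: about 6-8.5 points and about 7-11 points respectively at an assumed 10-25%.
- **Comparisons, item 4.** Replace the validation wording with: *to estimate the 28-day mortality risk difference with its 95% confidence interval and describe its consistency with the cited 1.5 points; a non-significant result is not a failure to replicate, and the comparison is non-randomized.* An interval that includes 1.5 and excludes zero may be described as consistent with the cited benefit.
- **Purpose.** Replace "without a significant increase in thromboembolic complications" with reporting the thromboembolic risk difference and its 95% confidence interval. Base any safety claim on the upper limit against an acceptable excess that the sponsor sets and justifies before analysis. If none is set, report the interval as descriptive and make no safety claim from non-significance.

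No extra patients are needed. The cost is that the stated claims become less favorable and that the sponsor must choose and defend a margin if it wants a safety claim. That choice is a new decision, not just an edit.

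### Non-randomized groups have no specified adjustment for severity: the regression is named but undefined, no injury severity score is on the data list, and post-dose values are labelled baseline

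*Combined protocol and SAP*

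**What the plan says.** **How the groups arise.** Under Design, Groups A, B and C are defined by who gives the first dose and where; for each, "200 patients shall be enrolled in this group in a prospective observational study format". Under Comparisons, eligible patients not treated in the field because they were "brought to the emergency department by agencies other than participating agencies will be assigned to the Group A". Group D is historical: patients "with similar injury severity and hemodynamics shall be randomly chosen from the previous five years of the trauma registry". No score, tolerance or matching method accompanies that sentence. The Comparisons section adds that controls must meet the same inclusion criteria as the treated patients.

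**What is compared.** The numbered list has A vs B, A vs C, B vs C, and A vs the control group. The Design section also has D compared with each of A, B and C. The primary outcome is mortality at 24 h, 48 h and 28 days.

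**How it is analysed.** Apart from the sample-size line, the Statistical analysis section reads "Statistical tests: Two-tailed T Test, Regression Analysis, Chi-Square Analysis". No model, covariates, weighting or matching is given anywhere.

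**What is recorded.** The Baseline characteristics list under Data collection has demographics, "Time of injury to TXA" for both doses, vital signs in "five sets (pre-hospital, during infusion, post-infusion, during second infusion, post-infusion", and "Glasgow Coma Scale (pre-treatment, 24 hours, 48 hours". Mechanism and area of injury appear under Analysis Measures. Neither list has an injury severity score.

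**The concern.** Transport mode, agency and calendar period can each plausibly track how badly the patient was hurt, the mechanism, and the distance and time to hospital. With no randomization, only selection, matching or analysis can separate these from the treatment contrast. The plan commits to no adjusted analysis, and a chi-square test is the natural choice for a binary primary outcome.

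Two features of the data list make this worse. The characteristic on which controls are to resemble treated patients is not itself recorded as a score. And the list headed baseline mixes pre-dose values with values measured during and after treatment. An analyst who completes the undefined regression from that list could condition on consequences of treatment. Time to the first dose is also the main feature that separates A from B and C, so adjusting for it would remove part of the contrast under study.

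At stake is the conclusion on mortality in the Purpose section, and the stated aim of using A vs D to validate CRASH-2.

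**Working it through.** **The plan's own figure.** The only planned number used here is 200 per group, from 95% confidence and a 10% margin. With p = 0.5 (assumed):
- One proportion: n = 1.96² × 0.25 / 0.10² = 96.04, so 97.
- Difference of two proportions: n = 2 × 1.96² × 0.25 / 0.10² = 192.07, so 193. With z rounded to 2 it is exactly 200.

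So 200 fits a 10% margin on a between-group difference after rounding, though the plan does not say so. Nothing below depends on how 200 was reached.

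**Count of items labelled baseline.** Of five vital-sign sets, one is pre-hospital and four are during or after an infusion. Of three Glasgow Coma Scale readings, one is pre-treatment and two are later. Time to TXA is listed for both doses. The infusion-based sets and time to TXA also have no counterpart in D, which has no study infusion.

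**Size of possible confounding.** The documents give no mortality or severity figures by group, so these inputs are assumed: no TXA effect, 200 per group, mortality 40% in severe and 8% in other patients, and 15% overall in the reference group. That last figure implies a severe share of (0.15 − 0.08)/0.32 = 21.9%.

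Spurious difference d = difference in severe share × (0.40 − 0.08):
- 5 points: 0.05 × 0.32 = 0.016, so 15% vs 16.6%.
- 15 points: 0.15 × 0.32 = 0.048, so 15% vs 19.8%.

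Rejection rate of the uncorrected two-sided 5% test = Φ((d − 1.96·SE₀)/SE₁) + Φ((−d − 1.96·SE₀)/SE₁), where SE₀ = √(2p̄(1 − p̄)/200) and SE₁ = √((p₁(1 − p₁) + p₂(1 − p₂))/200):
- 15% vs 16.6%: SE₀ = SE₁ = 0.0365; Φ(−1.522) + Φ(−2.399) = 0.072.
- 15% vs 19.8%: SE₀ = 0.0379, SE₁ = 0.0378; Φ(−0.695) + Φ(−3.233) = 0.244.

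**Range under other assumptions.** Mortality 5% in less severe patients and 20%, 30% or 40% in severe patients:

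| Severe share, two groups | Spurious difference (points) | Rejection rate |
|---|---|---|
| 50% vs 40% | 1.5, 2.5, 3.5 | 7.5%, 10.4%, 13.8% |
| 50% vs 30% | 3.0, 5.0, 7.0 | 16%, 29%, 43% |

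For scale, the Background section quotes a 1.5-point reduction in 28-day mortality from CRASH-2. In these examples an imbalance of 5 to 10 points in the severe share is enough to match it.

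**Information available for adjustment.** At an assumed 15% mortality, two groups of 200 give 400 × 0.15 = 60 deaths. Suppose every candidate variable entered with its listed categories: age (1 parameter), mechanism (3), area (4), systolic pressure (1), heart rate (1), Glasgow Coma Scale bands (2) and a severity score (1). That is 13 parameters before the group term, or 60/13 = 4.6 deaths each. A short set of age, two-level mechanism, systolic pressure, Glasgow Coma Scale bands and a severity score uses 6, plus 1 for group: 60/7 = 8.6.

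**The case against.** Four stronger readings are tempting, and the documents do not support them.

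- *The plan is purely unadjusted.* Regression is one of the three methods named. It may be intended for adjustment; the fault is that nothing about it is specified.
- *Severity differences will be read as TXA effects.* Three of the four numbered comparisons are between groups that all receive TXA. A severity difference there would be misread as an effect of setting or timing. Only comparisons with D bear on TXA itself. No group data are given, so the existence, size and direction of any imbalance are unknown, and bias could hide an effect as well as create one.
- *Similarity of the controls can be neither achieved nor checked.* D is also chosen on hemodynamics and must meet the same inclusion criteria. Mechanism, area of injury, pre-hospital vital signs and pre-treatment Glasgow Coma Scale are recorded. These are partial measures of severity. The registry may hold a score, but the documents do not say.
- *The plan intends to adjust for post-dose values.* The list is a data-collection list, and nothing makes its items covariates. Headings are loose throughout: Analysis Measures also mixes mechanism and area of injury with outcomes. The label is a risk, not a stated analysis.

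The illustration is also open to challenge. Its inputs are assumed, and the smaller imbalance moves the error rate only from 5% to about 7%.

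What remains is enough. No adjusted analysis is committed to, the recorded proxies do not measure anatomic severity, and the baseline label points an analyst towards the wrong covariates.

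**Conclusion.** The point holds and should be settled before outcomes are examined. Every comparison is between non-randomized groups. The plan leaves an unadjusted test as the default for the primary outcome, lists no severity score although controls are selected on severity, and labels post-dose values as baseline. Severity differences may therefore be read as an effect of TXA in comparisons with D, or of its setting or timing among A, B and C.

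The size cannot be derived from the documents. The false-positive rates of about 7% and 24%, and the wider range of 7.5% to 43%, rest entirely on assumed mortality rates and severity imbalances. They show only that moderate imbalance can produce differences as large as the effect the study hopes to confirm.

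**What to change.** 1. Make the 24 h, 48 h and 28-day mortality comparisons adjusted. Use propensity weighting, or a logistic or modified Poisson model, and state outcome, covariates and model for each comparison. A workable set is age, mechanism collapsed to blunt vs penetrating (stating where combined injuries and amputations go), pre-treatment systolic pressure, pre-treatment Glasgow Coma Scale and a severity score.
2. Add one injury severity score for all four groups, taken from the registry if it holds one (an assumption) and otherwise abstracted from the chart.
3. Restrict baseline to pre-dose values, with first recorded values for D. Do not adjust for time to TXA or any post-dose value; analyse time to TXA separately as an exposure.
4. Select D by matching or weighting on the same variables, state the method, and report balance for every comparison.
5. Report chi-square and t-tests as unadjusted description.

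**Cost.** Analysis wording, one extra data field, and chart abstraction if the registry lacks a score. Dosing and clinical care are unaffected.

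**Downsides.** With about 60 deaths per comparison at the assumed 15% mortality, and no more at 24 h and 48 h than at 28 days, the covariate set must stay small. Adjustment also does not remove the difference in era between D and the prospective groups, which should be stated as a limitation.
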